8.1.4 Overdose

An overdose is defined as a known, deliberate, or accidental administration of an investigational drug, to or by a study subject, at a dose above that assigned to that individual subject according to the study protocol.

All cases of overdose (with or without associated AEs) will be documented on an Overdose page of the eCRF, in order to capture this important safety information consistently in the database. Cases of overdose without manifested signs or symptoms are not considered AEs. AEs associated with an overdose will be documented on AE eCRF(s) according to Section 9.7.2, PTEs and AEs.

Serious adverse events (SAEs) associated with an overdose should be reported according to the procedure outlined in Section 9.7.4, Collection and Reporting of SAEs.

In the event of an overdose, supportive measures should be employed as needed, e.g., administration of supportive therapy as dictated by the subject's clinical status, removal of unabsorbed material from the gastrointestinal tract, or initiation of additional clinical monitoring.

8.2 Investigational Drug Assignment and Dispensing Procedures

Subjects will be assigned to receive a unique randomization number.

The clinical site will use the unique identifier to facilitate the pre-labeling of PK samples. It should also be contained on the PK transport vials shipped to the bioanalytical laboratory and will be used by the laboratory to report the subject data results. This unique identifier should only be used for the purposes described in this section. This identifier will be assigned upon randomization in the order in which subjects receive their first dose of the study drug.

8.3 Randomization Code Creation and Storage

The sponsor or their designee will generate the randomization schedule and provide a copy to the site pharmacist and bioanalytical laboratory prior to the start of the study. All randomization information will be stored in a secured area, accessible only by authorized personnel.

8.4 Investigational Drug Blind Maintenance

The investigational drug blind is maintained through a randomization schedule held by the dispensing pharmacist.

8.5 Unblinding Procedure

The investigational drug blind shall not be broken by the investigative staff unless information concerning the investigational drug is necessary for the medical treatment of the subject. All study assessments and causality assessments should be performed, if possible, prior to unblinding. In the event of a medical emergency, if possible, the medical monitor should be contacted to discuss the need for unblinding before the investigational drug blind is broken.

Unblinding envelopes will be supplied to the site prior to the first subject dosing and stored in a central and secure place to ensure access in the event of an emergency. Study staff will be trained on unblinding procedures.

The sponsor must be notified as soon as possible if the investigational drug blind is broken. The date, time, and reason the blind is broken must be recorded in the source documents, and the same information (except the time) must be recorded on the eCRF.

If any site personnel inadvertently become unblinded, the sponsor must be notified, and the SRG will determine whether to discontinue dosing or withdraw from the study of all affected subjects.

No change should be made to any assessment of the subject after unblinding.

Following assessment of the AE data and pre-defined criteria for study termination, dose escalation may be interrupted/stopped and the blind broken for further analysis. Based on a review of unblinded data, the sponsor, in consultation with the Investigator, will decide if and how it is appropriate for the study to proceed.

The Randomization schedule for all subjects will be released for analysis after the database for these cohorts is locked. The Investigator will be unblinded after database lock for all the cohorts if necessary.

8.6 Accountability and Destruction of Sponsor-Supplied Drugs

Drug supplies will be counted and reconciled at the site before being returned to the sponsor or designee or being destroyed.

The investigator or designee must ensure that the study medication is used in accordance with the approved protocol and is dispensed only to subjects enrolled in the study. To document appropriate use of study medication, the investigator must maintain records of all study medication delivery to the site, site inventory used by each subject, and return to the sponsor or designee.

Upon receipt of study medication, the investigator or designee must verify the contents of the shipments against the packing list, ensure the quantity is correct, and the medication is received within the labeled storage conditions. If quantity and conditions are acceptable, the investigator or designee should acknowledge the receipt of the shipment by signing the bottom half of the packing list and send via email and per instructions provided on the form. If any discrepancies exist between the packing list and the actual product received, the sponsor must be contacted to resolve the issue. The packing list should be filed in the investigator's essential document file. The investigator must maintain 100% accountability for all study medication received and dispensed during their entire participation in the study. Proper drug accountability includes, but is not limited to:

- Continuously monitoring expiration dates
- Frequently verifying that actual inventory matches documented inventory
- Verifying that the log is completed for the drug lot used to prepare each dose
- Verifying that all containers used are documented accurately on the log
- Verifying that required fields are completed accurately and legibly

If any dispensing errors or discrepancies are discovered, the sponsor must be notified immediately.

The investigator or designee must record the current inventory of all study medication on a sponsor-approved drug accountability log. The following information will be recorded at a minimum: protocol number and title, name of the Investigator, site identifier and number, description of study medication, expiry date, and amount dispensed, including the initials of the person dispensing and receiving the study medication. The log should include all required information as a separate entry for each subject to whom study medication is dispensed.

Prior to site closure or at appropriate intervals, a representative from the sponsor or its designee will perform clinical study material accountability and reconciliation before clinical study materials are returned to the sponsor or its designee for destruction or destroyed at the site, as applicable. The investigator will retain the original documentation regarding clinical study material accountability, return, and/or destruction, and copies will be sent to the sponsor or designee.

The investigator will be notified of any expiry date or retest date extension of clinical study material during the study conduct. On expiry date notification from the sponsor or designee, the site must complete all instructions outlined in the notification, including segregation of expired clinical study material for return to the sponsor or its designee for destruction.

9.0 STUDY PLAN

9.1 Study Procedures

The following sections describe the study procedures and data to be collected. For each procedure, subjects are to be assessed by the same investigator or site personnel whenever possible. The Schedule of Study Procedures is located in [Appendix A](#).

9.1.1 Informed Consent Procedure

The requirements of the ICF are described in Section [14.2](#).

The ICF must be obtained prior to the subject entering the study and before any protocol-related procedures are performed.

A unique subject screening number (of the form xx-xxx), the first two numbers for the site, subsequent three numbers for subject identification will be assigned to each subject when the ICF is obtained. This subject ID will be used until the subject is assigned their 4-digit randomization number.

9.1.1.1 Pharmacogenomic and Cerebrospinal Fluid Informed Consent Procedure

Pharmacogenomics and cerebrospinal fluid informed consent is a component of the overall study ICF. The requirements are described in Section [14.2](#).

The pharmacogenomic and (for applicable cohorts) cerebrospinal fluid sample collection is mandatory.

9.1.2 Demographics, Medical History, and Medication History Procedure

Demographic information to be obtained will include date of birth, sex, ethnicity, race as described by the subject, smoking status, and caffeine consumption at Screening.

Medical history to be obtained will include determining whether the subject has any significant conditions or diseases that stopped at or prior to signing the ICF. Ongoing conditions are considered concurrent medical conditions (see Section [9.1.7](#)).

Medication history information to be obtained includes any medication relevant to eligibility criteria stopped at or within 28 days before signing ICF.

9.1.3 Physical Examination Procedure

A physical examination performed by the investigator or medical officer consist of the following body systems: (1) eyes; (2) ears, nose, throat; (3) cardiovascular system; (4) respiratory system; (5) gastrointestinal system; (6) dermatologic system; (7) extremities; (8) musculoskeletal system; (9) nervous system; (10) lymph nodes; (11) abbreviated neurological exam; and (12) other.

Any abnormal change from the baseline physical examination (Screening and Inpatient Check-in [Day -1]) must be assessed as not CS or CS by the investigator and recorded in the source document and eCRF.

All CS findings/changes, as determined by the investigator, from the baseline physical examination will be recorded as a PTE or concurrent medical condition in the source document and on the appropriate eCRF described in Section 9.8.1 or Section 9.8.2.

On subsequent examinations, any abnormal change from the pretreatment physical examination assessment occurring immediately prior to the start of the investigational drug Inpatient Check-in (Day -1) must be assessed as not clinically significant (NCS) or CS by the investigator and recorded in the source document and eCRF. Any CS change or new diagnosis as a result of a CS change, as determined by the investigator, will be recorded as an AE in source documentation and on the PTE/AE eCRF.

9.1.4 Weight, Height, and BMI

A subject should have weight and height measured while wearing indoor clothing and with shoes off. The BMI is calculated using metric units with the formula provided below:

Height is recorded centimeters without decimal places, and for weight, it is kilograms (kg) with 1 decimal place. BMI should be derived as:

$$\text{Metric: BMI} = \text{weight (kg)} / [\text{height (m)}]^2$$

Results for BMI will be expressed with 1 decimal place.

Example:

Height=176 cm (or 1.76 m), weight=79.2 kg; $\text{BMI} = 79.2 / 1.76^2 = 25.57 \text{ kg/m}^2$ captured as 25.6 kg/m².

9.1.5 Vital Sign Procedure

Vital signs will include tympanic body temperature, respiration, pulse, and blood pressure and be collected at timepoints specified in the Schedule of Study Procedures ([Appendix A](#)). For eligibility determination, the pulse will not be derived from ECG. Pulse and blood pressure will be measured after at least 5 minutes supine and again after 2 minutes standing.

Vital signs should be measured at the same time (+/- 1 hour) of the day across visits if possible. When vital signs are scheduled at the same time as blood draws, the blood draw will take priority, and vital signs will be obtained within approximately 0.25 hours before or after the scheduled blood draw.

9.1.6 Documentation of Concomitant Medications

Concomitant medication is any drug given in addition to the study medication. These may be prescribed by a physician or obtained by the subject over the counter. Concomitant medication is not provided by the sponsor. At each study visit, subjects will be asked whether they have taken any medication other than the study medication (used from signing of ICF through the end of the study), and all medication, including vitamin supplements, over-the-counter medications, and oral herbal preparations, must be recorded in the eCRF. Documentation will include generic medication name, dose, unit, frequency, route of administration, start and end dates, and reason for use.

9.1.7 Documentation of Concurrent Medical Conditions

Concurrent medical conditions are those significant ongoing conditions or diseases that are present at the signing of ICF. This includes CS laboratory, ECG, or physical examination abnormalities noted at Screening examination. The condition (i.e., diagnosis) should be described.

9.1.8 ECG Procedure

Standard 12-lead ECGs will be recorded at timepoints specified in the Schedule of Study Procedures ([Appendix A](#)). Triplicate ECGs will be taken at each scheduled time. Additional unscheduled ECGs may be recorded where clinically necessary for subject safety.

When an ECG is scheduled at the same time as blood draws or vital signs, then the blood draws and vital signs will take priority, and the ECG will be obtained within 0.5 hour before or after the scheduled blood draw/vital sign assessment. If an ECG coincides with a meal, ECG will take precedence, followed by the meal.

All stationary 12-lead ECG machines will be supplied by the site. Subjects should be in a supine position following an approximate 10-minute rest period for ECG recordings. Should technical difficulties occur during the recording of the ECG, a reasonable attempt should be made to repeat the ECG shortly after the failed attempt.

ECGs will be read automatically, and also, the investigator or sub-investigator will manually interpret the ECG using 1 of the following categories: within normal limits, abnormal but not CS, or abnormal and CS. Abnormal QTc readings will be manually recalculated and reported by the Investigator on the eCRF. All 12-lead ECGs will be stored for manual measurement of intervals, if necessary. Twelve-lead ECGs will be recorded using an ECG machine that automatically calculates the heart rate and measures PR interval, RR interval, QRS interval, QT interval, and QTcF and QTcB (Fridericia's and Bazett's correction) intervals. Paper ECG traces will be recorded for 10 seconds at a standard paper speed of 25 mm/sec, and gain of 10 m/mV or digital recordings will be used.

One copy of the 12-lead ECG with the physician's signature and date of assessment will be filed with the source documents and captured in the appropriate eCRF. If the original ECG is printed on thermal paper, the ECG report must be photocopied and certified. The photocopy will be filed with the original ECG in the source.

All ECGs will be recorded at the time points detailed in [Appendix A](#).

9.1.9 Pharmacogenomic Sample Collection

Every subject must sign ICF/be consented to the sampling of whole blood for pharmacogenomic analysis to participate in the study.

One whole blood sample for DNA isolation and genotyping will be collected at time points specified in the Schedule of Study Procedures ([Appendix A](#)) into plastic dipotassium ethylenediamine-tetra acetic acid (K₂EDTA) spray-coated tubes and stored under frozen conditions. In addition, two whole blood samples will be collected at time points specified in the Schedule of Study Procedures ([Appendix A](#)) for ribonucleic acid (RNA) pharmacogenomic analysis. The pre-dose RNA blood samples should be collected under fasted conditions and prior to any other blood collection.

DNA may be evaluated for the genetic contribution to how the drug is broken down or affects the body. This is called a “pharmacogenomics research study.” Specific purposes of this study include:

- Identifying genetic reasons why certain people respond differently to CVN766
- Finding out more information about how CVN766 works
- Generating information needed for research, development, and regulatory approval of tests to predict response to CVN766
- Identifying variations in genes related to the biological target of CVN766

This information may be used, for example, to develop a better understanding of the safety and efficacy of CVN766 and other study medications and for improving the efficiency, design, and study methods of future research studies.

The samples will be stored no longer than 15 years after completion of the CVN766 study and/or until the drug development of CVN766 is no longer actively pursued by the sponsor or its collaborators. No samples will be stored for longer than permitted by the applicable law, and samples will be destroyed upon notification from the sponsor. “Stored samples” in this context are defined as samples that are double coded (the samples are stripped of all personal identifying information but a key links the samples to the clinical data collected from the sample donor) and are used in the analysis of investigational drug or related drug.

The sampling of whole blood for pharmacogenomic and genotyping analysis is mandatory; every subject must sign the ICF in order to participate in this study. DNA samples will be collected and may be used to evaluate drug metabolic enzyme and transporter polymorphisms that may contribute to the variability in the PK of CVN766. Also, since pharmacogenomics is an evolving science, many genes and their functions are not yet fully understood. Future data may suggest a role of some of these genes in drug response, which may lead to additional hypothesis-generating exploratory research and diagnostic development on stored samples.

If necessary and feasible, a second aliquot of blood may be taken if isolation of DNA and RNA from the first sample was not successful or possible.

Samples will be frozen at -70°C or lower and shipped separately on dry ice prior to extraction and storage at -70°C or lower. Samples should not be allowed to thaw until processed.

Detailed instructions for the handling and shipping of samples are provided in a separate lab manual.

Genotyping on collected samples may be deferred until after the completion of the study’s in-life activities.

Each pharmacogenomic sample for a study subject should be identifiable on the requisition form with the 4-digit randomization number.

9.1.10 PK Sample Collection

9.1.10.1 Collection of Blood for PK Sampling

Blood samples for analysis of CVN766 plasma concentrations will be collected into chilled Vacutainers containing K₂EDTA according to the schedule in [Appendix A](#). Instructions for sample processing and shipment are provided in a separate lab manual.

In all single-dose cohorts, serial blood samples to determine CVN766 concentrations in plasma will be collected according to Table 7.

Table 6 Collection of Blood Samples for PK Analysis in Single-Dose Cohorts

Sample Type	Dosing Day	Time Post-dose (hours).
Plasma	1	Pre-dose (within 15 minutes prior to dosing) and at 0.5, 1, 1.5, 2, 3, 5, 8, 12, 16, 24-, 36-, 48-, and 72-hours post-dose.

In all cohorts for Part 2, serial blood samples for determination of CVN766 concentrations in plasma will be collected according to Table 7.

Table 7 Collection of Blood Samples for PK Analysis in Multiple-Dose Cohorts

Sample Type	Dosing Day	Time Post-dose (hours).
Plasma	1	Pre-dose (within 15 minutes prior to dosing) and at 0.5, 1, 1.5, 2, 3, 5, 8, 12, 16, and 24 (Day 2 pre-dose) hours post-dose.
	3,4,5,6	Pre-dose (within 15 minutes prior to dosing)
	7	Pre-dose (within 15 minutes prior to dosing) and at 0.5, 1, 1.5, 2, 3, 5, 8, 12, 16, 24, 36, 48, and 72 ^(a) hours post-dose.

(a) If emerging PK data indicate the CVN766 $t_{1/2}$ is 15 hours (or less), the 72-hour timepoint is unnecessary.

The PK samples will be collected at the nominal time point; all other assessments will be collected, before or after, within the allowable windows. The actual time of sample collection will be recorded on the source document and eCRF.

Sampling time points may be adjusted or added based on the preliminary emerging PK data collected from prior cohort(s). Still, the total number of samples collected per subject should not exceed the planned number by more than 4.

Placebo samples will not be analyzed by the bioanalytical laboratory except 2 samples per subject receiving placebo, 1 pre-dose, and the other around the expected time at which C_{max} occurred (as emerging from the actual measurement of the samples of the first dose group) to ensure from a safety perspective that no additional subjects could have been on active treatment.

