To assess the effect of food on bioavailability of CVN766 in suspension formulation, single-dose administration will be repeated in a single cohort after ingestion of a standardized high-fat high-calorie meal according to FDA Guidance for Industry (Food-effect bioavailability and fed bioequivalence studies, Dec 2002). Once the safety of the S3 cohort dose level has been assessed, the S3 cohort subjects will return to the clinic (no sooner than 14 days after their prior dose, or at least 4 half-lives has lapsed based on preliminary PK data, whichever is longer) and will receive the same dose as before, administered after ingesting a standardized breakfast. Subjects will finish the entire content of their breakfast within 25 minutes and will receive an investigational product 30 minutes (\pm 5 minutes) after beginning the meal. Sentinel dosing will not be required for subjects returning to the clinic for the fed regimen. If the CVN766 PK parameters in the fasted S3 cohort reveal poor absorption with inconclusive results, the fed cohort will be deferred until a higher dose level.

An outline of the single-dose study visit schedule is included in [Table 1](#). A Schedule of Study Procedures is listed in [Appendix A](#).

Table 1 Single-Dose Visit Schedule

Screening ^a	Inpatient Check-in	Dosing, PK, CSF & Safety Assessments ^b	Inpatient PK & Safety Assessments	Inpatient Discharge ^c	Follow-Up Outpatient Visit	Follow-Up Call ^d
Day -28 to -2	Day -1	Day 1	Day 2-4	Day 4	Day 8 \pm 1 day	Day 14 \pm 2 days

- (a) Screening will occur at study entry. Subjects returning for the “Fed” repetition of the single-dose regimen will not undergo Screening assessments except as required at Day -1.
- (b) CSF collection will apply only to cohort S3 (fasted).
- (c) Discharge from the clinic may be delayed if necessary to continue monitoring for resolution of AEs.
- (d) The final follow-up assessment will occur by telephone unless abnormal CS findings are observed upon discharge. In these cases, subjects must return to the clinic for re-evaluation.

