6.1.2 Part 2: Multiple-Dose Regimen

For the multiple-dose regimen, approximately 24 subjects will be enrolled in 1 of the 3 multiple-dose cohorts (designated as M1 through M3, respectively) in an ascending fashion. Dosing will be administered in the fasting state; this can be changed by the SRG if exposure is found to be higher in the fed state. The dose levels planned to be studied in the multiple-dose regimen (M1 through M3) are provided in Table 5. Each multiple-dose cohort will consist of 8 subjects randomized to CVN766 or placebo, whereby 6 subjects will receive a daily dose of CVN766, and 2 subjects will receive matching placebo for 7 days. However, the duration may be increased to ≤14 days at the discretion of the safety review group (SRG) if preliminary PK data suggest steady-state will not be achieved within 6 days of daily dosing. Unlike the single-dose regimen, sentinel dosing within cohorts is not required in the multiple-dose regimen.

Subjects for all multiple-dose cohorts will be admitted to the study unit 1 day prior to dosing and remain in the unit for the duration of the dosing period and for at least 48 hours after the last dose for safety and PK assessments before discharge. On treatment Days 1 and 7, subjects will undergo safety monitoring and PK sampling from blood plasma through 48 hours post-dose and, in cohort M1 only, from urine through 24 hours post-dose. In cohorts M1 and M2, on treatment Day 7 (or last day of dosing, if extended beyond Day 7), subjects will additionally undergo PK sampling from CSF via lumbar puncture at 3 hours post-dose. If needed to resolve questions arising from prior cohorts' data, subjects in cohort M3 also may, at SRG discretion, undergo PK sampling from CSF via lumbar puncture, the choice of day (e.g., Day 1 or Day 7) and sampling time to be decided by SRG. Subjects in MAD cohorts may be asked to return to the clinic for an additional plasma PK sample 3 days after the last dose (e.g., Day 10) depending on emerging PK data, i.e., $t_{1/2}$. The total confinement period will be 9 nights unless extended for additional dosing days or for management of AEs. Follow-up assessments will occur approximately 7 and 14 days after the final dose. A summary of multiple-dose study visits is included in Appendix A.

Table 2 Multiple Dose Visit Schedule

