8.1.1 Dosage Form, Manufacturing, Packaging, and Labeling

Study drug refers to CVN766 and matching placebo. Study drug will be provided in bulk supply. An unblinded pharmacist will manage and prepare doses as oral suspensions as needed throughout the study.

In this protocol, the term study medication refers to all or any of the drugs defined below.

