8.1.3 Dose and Regimen

The investigator or investigator's designee will instruct the subject on dosing procedures.

All dosing will occur while subjects are in the clinic under the supervision of the Investigator and in fed or fasting conditions as outlined in Section 7.4.

The exact time of dose will be recorded in the source documents and on the appropriate eCRF.

The planned dose levels to be studied are provided in Table 5. If the planned highest dose level does not reach the desired exposure, then additional cohorts with higher dose levels may be considered. If all planned dose levels are not tolerated in an earlier cohort, the following cohorts may study lower doses at the discretion of the Investigator and the SRG. The actual choice of the subsequent dose level will occur after a full review of the available blinded safety, tolerability, and clinical laboratory results, and available PK data in the preceding cohort. The subsequent dose level may be higher, lower, or remain the same as the preceding dose level.

Table 5 describes the treatment and medication type that would be provided for each cohort.

Table 5 Planned Single and Multiple Dose Levels by Cohort

Single-Dose Cohorts			
Cohort	Planned Treatment*	No. of Subjects	Medication Type
S1	CVN766 5 mg	6	oral suspension
	Placebo	2	oral suspension
S2	CVN766 15 mg	6	oral suspension
	Placebo	2	oral suspension
S3 Fasted	CVN766 45 mg	6	oral suspension
	Placebo	2	oral suspension
S3 Fed (Same 8 subjects as in the S3 FASTED cohort)	CVN766 45 mg	6	oral suspension
	Placebo	2	oral suspension
S4	CVN766 125 mg	6	oral suspension
	Placebo	2	oral suspension
S5	CVN766 250 mg	6	oral suspension
	Placebo	2	oral suspension
Multiple Dose Cohorts			
Cohort	Planned Treatment*	No. of Subjects	Medication Type
M1	CVN766 45 mg	6	oral suspension
	Placebo	2	oral suspension
M2	CVN766 125 mg	6	oral suspension
	Placebo	2	oral suspension
M3	CVN766 250 mg	6	oral suspension
	Placebo	2	oral suspension

* Dose (active or placebo) is in 10 mL of suspension.

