12.3 Determination of Sample Size

The sample size chosen of 8 subjects per cohort (6 active: 2 placebo) is considered to be sufficient for the evaluation of the safety, tolerability, and PK of each cohort. The sample size was not based on statistical power considerations.

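### The placebo assay rule counts samples per subject, so for the S3 and multiple-dose placebo subjects, who are dosed more than once, it cannot give the assurance it states

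*Protocol*

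**What the plan says.** Section 9.1.10.1 is the only visible place that sets which placebo samples are assayed. None are, "except 2 samples per subject receiving placebo, 1 pre-dose, and the other around the expected time at which C"max is reached. The stated purpose is "to ensure from a safety perspective that no additional subjects could have been on active treatment". The count is per subject. The section does not say which day or period supplies the two samples, nor that both must come from the same dosing occasion.

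Two groups of placebo subjects are dosed more than once:

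- **S3.** Table 5 in Section 8.1.3 lists the fed regimen as "S3 Fed (Same 8 subjects as in the S3 FASTED cohort"), so its 2 placebo subjects are dosed in both periods. Section 6.1.1 has them return "no sooner than 14 days after their prior dose, or at least 4 half-lives has lapsed based on preliminary PK data, whichever is longer".
- **M1 to M3.** Under Section 6.1.2, "6 subjects will receive a daily dose of CVN766, and 2 subjects will receive matching placebo for 7 days", and the course may be extended to at most 14 days.

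Doses are made up at the site: "An unblinded pharmacist will manage and prepare doses as oral suspensions as needed throughout the study" (Section 8.1.1). Section 8.3 gives the bioanalytical laboratory a copy of the randomization schedule.

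**The concern.** A pre-dose and a near-peak sample are a sound check for a subject dosed once. For a subject dosed twice, or seven times, they hold one post-dose sample between them. A pre-dose sample cannot show drug given afterwards, and a near-peak sample shows mainly the dose just taken. Because doses are compounded repeatedly, an error confined to one administration is possible, and the rule was not written with that case in view.

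What is at stake is the placebo comparator. The four primary endpoints in Section 5.2.1 are percentages of subjects with an adverse event or a clinically significant laboratory, ECG or vital-sign result. A placebo subject who had unknowingly received CVN766 would contribute any resulting event as placebo background, which would narrow the apparent contrast with active treatment.

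**Working it through.** The protocol gives no calculated figure to reproduce. The check counts administrations against assayed samples and then asks how long one misplaced dose stays visible.

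**Inputs**

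- Allocation: 6 active and 2 placebo per cohort (Section 12.3), with 5 single-dose and 3 multiple-dose cohorts (Table 5).
- Near-peak placebo samples assayed: 1 per placebo subject (Section 9.1.10.1).
- Half-life: up to 6.5 h projected from animals (Section 6.2). As an upper scenario, 15 h, the threshold at which Section 9.1.10.1 drops the 72-hour sample.
- Assay limit: not given. Assumed range: 0.1% to 10% of the single-dose concentration at the same post-dose time.

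**Coverage**

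- Placebo subjects: 5 × 2 + 3 × 2 = 16, of whom 2 (S3) + 6 (multiple-dose) = 8 are dosed more than once.
- Placebo administrations: 10 single-dose + 2 S3 fed + 3 × 2 × 7 = 42 multiple-dose, total 54.
- Near-peak samples assayed: 16, and 16/54 = 29.6%. Within S3 and the multiple-dose cohorts: 8/46 = 17.4%.
- With 14-day dosing: 10 + 2 + 84 = 96 administrations, and 16/96 = 16.7%.

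**Visibility of one misplaced dose**, residual = 0.5^(elapsed time / half-life)

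*S3.* Fourteen days is 336 h. The residual is 0.5^(336/6.5), about 3 × 10⁻¹⁴ %, or 0.5^(336/15), about 2 × 10⁻⁵ %. A fasted-period dose would therefore not be expected to show in a fed-period sample, and a fed-period dose cannot show in a fasted-period one.

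*Multiple-dose, samples taken on Day 1.* A dose on any of Days 2 to 7 comes after the samples and cannot be seen. One day in seven is tested.

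*Multiple-dose, samples taken on Day 7.* Earlier doses may still be visible:

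| Dose given | Residual, 6.5 h | Residual, 15 h |
|---|---|---|
| 24 h earlier | 7.7% | 33% |
| 48 h earlier | 0.6% | 10.9% |
| 72 h earlier | 0.05% | 3.6% |
| 144 h earlier | 0.00002% | 0.13% |

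Number of the 7 dosing days on which a single misplaced dose would be detected:

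| Assumed assay limit | 6.5 h | 15 h |
|---|---|---|
| 10% | 1 | 3 |
| 5% | 2 | 3 |
| 1% | 2 | 5 |
| 0.1% | 3 | 7 |

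**Weight of one subject.** The Study Summary (Statistical Considerations) pools placebo across single-dose cohorts and, separately, across multiple-dose cohorts. One misdosed subject is 1/10 = 10% of the first pool or 1/6 = 17% of the second.

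**The case against.** The strongest reply is that the stated purpose concerns subjects, not administrations. On its plainest reading the rule checks allocation, and a subject wrongly on CVN766 for the whole course would be found. That stands. But the purpose is worded as an assurance that no further subject could have been on active drug, and a subject dosed with it in one S3 period would have been.

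Other safeguards also exist. Active subjects' samples are assayed in full, so if two doses were exchanged, the active partner's profile may show missing or lowered concentrations. Section 8.6 requires a log of the drug lot for each dose, separate entries per subject, full accountability and immediate notice of dispensing errors. These reduce the risk. What remains is CVN766 prepared in place of placebo with no matching gap in an active subject and no trace in the log.

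Four stronger readings are tempting and not supported:

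- **That a single-occasion error in a multiple-dose subject always escapes.** The sampling day is open, and a Day 7 sample can carry drug from Day 6 and perhaps earlier.
- **That the 70% of administrations without a near-peak assay is a miss probability.** It is a coverage share. It ignores carry-over and the other controls, and the protocol gives no error rate.
- **That one S3 error would contaminate half of a fed placebo group.** The fasted/fed split in the Study Summary applies to the CVN766 dose levels. Single-dose placebo is pooled.
- **That timing the near-peak sample from the first dose group defeats the check.** Detection needs a quantifiable level, not the exact peak, and nothing in the protocol shows that a fed dose would be unquantifiable then.

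**Conclusion.** The point holds in limited form. The rule suits subjects dosed once and detects continuous misallocation. For the 8 placebo subjects dosed repeatedly it cannot support its stated assurance, because it fixes neither day nor period and assays one near-peak sample per subject.

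The S3 gap holds across the half-lives the protocol mentions. The multiple-dose gap covers Days 2 to 7 if the samples come from Day 1. If they come from Day 7, it ranges from six undetected days (6.5 h half-life, 10% limit) to none (15 h, 0.1% limit). These figures assume first-order decline, a single misplaced dose and the assay limits shown.

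The consequence is possible misclassification of 1 in 10 or 1 in 6 placebo subjects in descriptive summaries. No hypothesis test against placebo is affected. The change is worth making because the comparator is small and the samples are already drawn.

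**What to change.** In Section 9.1.10.1, change the count from two samples per placebo subject to two samples (pre-dose and near expected Cmax) per placebo subject:

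- for each S3 dosing period, fasted and fed; and
- for each intensive PK day in the multiple-dose cohorts, meaning the first and last dosing days.

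This adds (2 S3 + 6 multiple-dose subjects) × 2 = 16 assays and raises near-peak coverage from 16 to 24 samples.

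Optionally, also assay the multiple-dose pre-dose samples already collected between those days: 6 subjects × 5 (Days 2 to 6) = 30 more for a 7-day course, plus any collected if dosing is extended. In a 7-day course every multiple-dose administration would then have an assayed sample within 24 hours. At 24 hours 7.7% (6.5 h) to 33% (15 h) remains, so the value of this option depends on the assay limit, which should be stated.

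The cost is a small amount of bioanalytical work. No new blood draws, visits or subjects are needed, and no new unblinding, since the laboratory already holds the randomization schedule.
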